## **8 DATA COLLECTION& MANAGEMENT**

### **8.1 DATA COLLECTION**

Data management will be conducted in compliance with TASC SOPs on Data Management. The data will be principally collected by the nurses appointed to the trial and supported by other trial appointed staff. The data sources will include the CRF, medical notes, laboratory reports and trial specific questionnaires.

Trial-specific data will be collected at baseline, randomisation week 4, week 8 (HCV genotype 1), end of treatment and 12 weeks post treatment.

Most of this data will be entered directly into the CRFs without being routinely recorded in clinical data sources. Participants will be asked to consent to information being collected at routine annual clinic visits for up to 5 years to check for reinfection.

### **8.2 DATA MANAGEMENT SYSTEM**

The data management system provided by TCTU will be OpenClinica. Development and validation of the trial database with QC and extraction of data will be done according to TCTU procedures. The DMS will be based on the protocol and case report form (CRF) for the trial and individual requirements of the investigators. The CRF will collect only information that is required to meet the aims of the trial and to ensure the eligibility and safety of the participant. The CI may delegate CRF completion but is responsible for completeness, plausibility and consistency of the CRF. Any queries will be resolved by the CI or delegated member of the trial team. The trial database will be compliant with TASC SOPs on Creating and Managing Databases. Extracts for analysis will be based on the dummy data tables provided by the trial team.

## **9 STATISTICS AND DATA ANALYSIS**

### **9.1 SAMPLE SIZE CALCULATION**

Statistical analysis will be conducted in compliance with TASC SOPS.

We propose to conduct this project as a randomised trial to show that DAA therapy in very active PWIDs administered fortnightly with or without adherence intervention is non-inferior to DOT. We will compare pathways sequentially comparing DOT vs fortnightly delivery and then DOT versus fortnightly pickup with adherence intervention. Fortnightly pick up will be more cost effective than the other two options so long as adherence and efficacy matches that of the DOT and fortnightly plus adherence intervention. If we assume a 95% SVR rate (based on published studies) in the DOT arm of the trial in this population and a non-inferiority limit of 14% (which would be likely to maintain cost-effectiveness) then at a 5% significance level and 90% power

we would need a sample size of 42 in each group 126 in total. To allow for drop-outs we will aim to recruit 135 individuals, 45 per group.

A Statistical Analysis Plan (SAP) will be prepared for analysis of primary and secondary outcomes and will include a plan for handling missing data

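### The 90% power claimed for 42 per group needs an unstated one-sided 5% level and a normal approximation; at that level no valid test exceeds about 83% power at 42 or 85% at 45.

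*Protocol*

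**What the plan says.** Protocol section 9.1 sets out to show that DAA therapy "administered fortnightly with or without adherence intervention is non-inferior to DOT". Its planning inputs are:

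- DOT arm: "If we assume a 95% SVR rate (based on published studies) in the DOT arm of the trial in this population".
- Margin: "a non-inferiority limit of 14% (which would be likely to maintain cost-effectiveness").
- Error rate and power: "then at a 5% significance level and 90% power".
- Result: "we would need a sample size of 42 in each group 126 in total".
- Recruitment: "To allow for drop-outs we will aim to recruit 135 individuals, 45 per group".
- Comparisons: "We will compare pathways sequentially comparing DOT vs fortnightly delivery and then DOT versus fortnightly pickup with adherence intervention".

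The section does not say whether the 5% is one- or two-sided, and it does not give the SVR rate assumed in the fortnightly arms. Section 9.2.3 analyses SVR by logistic regression, uses everyone randomised to an arm as the denominator, and counts drop-outs and losses to follow-up as failures. Neither section names the test or interval that will be set against the 14-point margin.

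**The concern.** Two things make the stated pair of 5% and 90% doubtful. First, the side of the 5% matters for a non-inferiority test, and only one choice returns 42. Second, at 95% SVR each arm is expected to have only two or so failures (42 × 0.05 = 2.1; 45 × 0.05 = 2.25). The usual sample-size formula evaluates the variance at 95% in both arms, whereas at the edge of non-inferiority (95% v 81%) the variance is much larger.

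Non-inferiority of fortnightly dispensing is the trial's central claim. If 5% and 90% cannot both hold, then either the risk of missing a true non-inferiority is greater than the 10% stated, or the 90% is bought with more than 5% false non-inferiority claims.

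**Working it through.** **Inputs.** From section 9.1: DOT SVR 95%, margin 0.14, level 5%, power 90%, n = 42 (45 recruited). Assumed, because not stated: true SVR of 95% in the fortnightly arm as well. Each figure below is for one comparison with DOT.

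**1. Reproducing the plan's figure.** Unpooled normal approximation:

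n = (z_α + z_0.90)² × 2 × 0.95 × 0.05 / 0.14²

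- One-sided 5%: (1.645 + 1.2816)² × 0.095 / 0.0196 = 8.565 × 0.095 / 0.0196 = 41.5, so **42**. This matches.
- Two-sided 5%: (1.960 + 1.2816)² × 0.095 / 0.0196 = 10.508 × 0.095 / 0.0196 = 50.9, so 51. This does not match.

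Power by the same formula, Φ(0.14 / √(0.095/n) − z_α):

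| n per group | one-sided 5% | two-sided 5% |
|---|---|---|
| 42 | Φ(2.944 − 1.645) = 90.3% | Φ(2.944 − 1.960) = 83.7% |
| 45 | Φ(3.047 − 1.645) = 92.0% | Φ(3.047 − 1.960) = 86.1% |

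**2. Why the approximation is optimistic here.** The formula uses variance 2 × 0.95 × 0.05 = 0.095. At the null point of 95% v 81% it is 0.95 × 0.05 + 0.81 × 0.19 = 0.201. A score test uses the rates fitted under the null, here 97.25% and 83.25%, with variance 0.0267 + 0.1394 = 0.166. Putting that into the sample-size formula (Farrington-Manning) gives about 58 per group for 90% power at one-sided 5%, and about 73 at one-sided 2.5%.

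**3. Exact results.** Both binomials were enumerated in full. Power is at 95% v 95%. Type I error is given at 95% v 81% and as the maximum over all pairs of rates 14 points apart.

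| Nominal one-sided 5% | n | Power | Error at 95% v 81% | Maximum error |
|---|---|---|---|---|
| Wald | 42 | 91.2% | 7.7% | 14.2% |
| Wald | 45 | 89.9% | 6.3% | 10.8% |
| Score (Farrington-Manning) | 42 | 80.8% | 4.7% | 5.4% |
| Score (Farrington-Manning) | 45 | 84.7% | 4.7% | 5.3% |
| Newcombe | 42 | 80.8% | 4.7% | 5.4% |
| Newcombe | 45 | 84.7% | 4.7% | 5.6% |

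The maxima at 42 can be checked by hand. They occur when the true DOT rate is 100% and the fortnightly rate 86%. With no DOT failures, the Wald test accepts three fortnightly failures, since 3/42 + 1.645 × √(0.0714 × 0.9286 / 42) = 0.0714 + 0.0654 = 0.137, which is below 0.14. The chance of three or fewer failures in 42 at 14% is 0.0018 + 0.0121 + 0.0405 + 0.0879 = 0.142. The score and Newcombe tests stop at two failures: 0.0018 + 0.0121 + 0.0405 = 0.054.

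**4. An upper limit that does not depend on the test.** A linear program searched all tests, randomised ones included, whose error is at most the nominal level along the null boundary, for the highest power at 95% v 95%:

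| Level held | n = 42 | n = 45 |
|---|---|---|
| one-sided 5% | 82.7% | 85.4% |
| one-sided 2.5% | 71.9% | 75.5% |

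**5. One-sided 2.5% (a two-sided 95% interval).** The score test gives 69.2% (n = 42) and 68.4% (n = 45); Newcombe gives 70.1% and 74.2%. The range is therefore 68-74%.

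**The case against.** **The calculation is not wrong.** This stands. The stated inputs return 42 exactly from a standard formula. A reader might infer an arithmetic error; there is none.

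**The side can be recovered.** Non-inferiority is directional and only one-sided 5% yields 42, so a reader might not accept 51 per group as the true requirement. That is fair: the documents do not support saying that a two-sided 5% design was intended. The two-sided figures matter only because the text leaves the choice open and a two-sided 95% interval could still be reported.

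**No Wald test is planned.** Also true. Section 9.2.3 names logistic regression, and the interval may be set in the SAP, which is not at hand. A reader might infer that the trial will run at 7.7% or 6.3% type I error; the protocol does not say that. The limit in step 4 does not depend on the choice, however. It also covers a genotype-adjusted analysis under the same planning assumption: if SVR is 95% whatever the genotype, the two success counts carry all the information on the difference. The SAP cannot recover 90% at a true one-sided 5% with these numbers.

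**The alternatives are not perfectly exact either.** Score and Newcombe tests exceed 5% slightly at worst (5.3-5.6%). A strict exact unconditional test gives 75.7% at 42 and 84.7% at 45, so 81% at 42 is a little generous, while 85% at 45 is unaffected.

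**45 is the number that counts.** Under section 9.2.3 drop-outs stay in the denominator, so 45 per group are analysed and the shortfall is about 5 points (90% − 84.7%), not 9. That stands. The figure at 42 is relevant only if participants leave the denominator, as the modified intention-to-treat wording in the Summary would allow.

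**Conclusion.** The point holds. Section 9.1 pairs a 5% level with 90% power, and at 42 or 45 per group the two cannot both be true under the protocol's own assumptions. At one-sided 5%, power is about 85% at the 45 per group analysed (at most 85.4%) and about 81% at 42 (at most 82.7%). The chance of missing a true non-inferiority is thus about 15-19% rather than 10%. At one-sided 2.5% it is about 26-32%.

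The causes are an unstated side and a normal approximation used with about two expected failures per arm, not a miscalculation. The figures assume a true 95% SVR in both arms, a 14-point risk difference and a single comparison. Because drop-outs count as failures, any drop-out not already allowed for in the 95% lowers power further. The effect is moderate: it changes what the trial may claim about its power, not how it is run.

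**What to change.** In section 9.1, and in the SAP to match:

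1. State that the level is one-sided 5%, meaning that the lower limit of a two-sided 90% confidence interval for the risk difference (fortnightly minus DOT) is compared with −14 points, and that 95% SVR is assumed in every arm.
2. Base the non-inferiority conclusion on a score or Newcombe type interval. The logistic regression in section 9.2.3 can stay as the adjusted analysis alongside it.
3. Restate power as about 85% at 45 per group (about 81% at 42).
4. If a two-sided 95% interval will decide non-inferiority, state power as about 68-74% instead.

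Keep 135 participants. The cost is a change of wording and a less favourable stated power; recruitment, treatment and follow-up do not change.

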We will recruit 135 participants and randomise them to one of three arms: daily, directly observed therapy; fortnightly dispensing of drugs; fortnightly dispensing of drugs with a psychological adherence intervention. Randomisation will be stratified according to HCV genotype. Participants will be treated for 12 weeks and followed up 12 weeks post treatment for the measurement of sustained viral response (SVR). The primary outcome measure will be SVR at 12 weeks post treatment (SVR12), as this measure of cure is the determinant of sufficient compliance and efficacy within the 3 treatment arms. Analysis will be by modified intention to treat of all participants who receive one dose of therapy, to show non-inferiority fortnightly dispensing is easier to deliver than daily dispensing.

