## **4 TRIAL POPULATION**

### **4.1 NUMBER OF PARTICIPANTS**

This trial aims to treat 135 active PWID with active HCV infection in Tayside over a two year period. Due to the nature of this trial, trial dropouts are a trial endpoint and will not be replaced.

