## 5.5 RANDOMISATION

### 5.5.1 Randomisation

After successful screening for eligibility and safety, participants will be randomised to either DOT, fortnightly pick up or fortnightly pick up with psychological intervention.

PWID who are eligible for this trial have unpredictable and chaotic lives. It is therefore possible that an individual will consent to take part, provide baseline information and have blood taken for safety and eligibility checking. If eligible they may be randomised. They may then not be seen at the needle exchange for a number of weeks or even months. It is standard clinical practice that pretreatment bloods are valid for a period of 6 months and therefore we will consider baseline bloods taken for the study to be valid for 6 months unless there is a clinical indication to repeat within that period. Any clinical decision on whether bloods need to be repeated within 6 months will be made by the CI. If a consented participant reappears after a period longer than 6 months has elapsed, a documented verbal check will be made to confirm that the individual continues to consent to taking part in the study. The bloods will be re-taken and eligibility will be based on the results of these new blood tests. The blood tests taken closest to the date of treatment initiation will be considered as the baseline data. The viral genotype will not be retested as NHS lab policy is to redo this test only after 5 years have elapsed. After 6 months the baseline CRF will also be repeated to provide up-to-date pretreatment information. In this case, the information originally collected in the baseline CRF will be filed but will not be entered into the electronic data management system (Openclinica) and will not form part of the analysed dataset. To ensure that the correct, most up-to-date baseline data is entered into Openclinica, baseline data will be entered once each participant has started their treatment.

As this is an un-blinded trial, the nurse, or delegated member of staff, and participant will be aware of which arm they are allocated to. Randomisation to each of the three trial groups will be stratified by genotype so that the proportion of genotype 1 vs genotype 3 infected participants will be the same in each group. The Tayside Clinical Trials Unit (TCTU) GCP-compliant online randomisation system, TRuST, will be used by the specialist nurse or delegated, trained member of staff to perform the randomisation.

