## 9.2 PROPOSED ANALYSES

### 9.2.1 Primary Outcomes

- To compare using SVR rates the efficacy and compliance of DAAs in 135 new HCV positive individuals randomised to one of three groups; DOT, fortnightly therapy and fortnightly therapy with psychological adherence intervention.

The data for these outcomes will be generated directly from the CRFs from the clinical and laboratory data recorded therein.

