### 9.2.3 Statistical analysis

Outcomes Data Analysis plan: Analysis of the trial will follow the principles outlined in the ICH E9 'Statistical Principles for Clinical Trials' and carried out by the UKCRC registered Tayside

Clinical Trials Unit (TCTU). Prior to data lock an agreed Statistical Analysis Plan (SAP) will be finalised covering the pre-specified statistical analysis.

The primary outcome of SVR will be assessed as a binary outcome for subjects and so will utilise logistic regression modelling. The numerator will be the number of subjects achieving SVR and the denominator will be total number of patients randomised to each arm. Additionally results will be expressed as a proportion of the estimated HCV infected subjects in needle exchange. The estimated number of infected patients will be based on national survey data and the empirical rate discovered in the trial (allowing for patients who refuse testing). A test of interaction between contingency and pathway will be carried out and if not significant contingency will be assessed independently. If significant then the effect of contingency will be assessed by each pathway separately. As all patients will have either achieved SVR or not and we will assume that drop-outs / lost to follow-up are failures, there will be no missing data in the primary outcome. Extra- binomial variability or over-dispersion will be examined in the logistic model and if present alternative modelling such as negative binomial models will be considered. This will also be adjusted by therapy and genotype; the two factors are interdependent determining length of therapy.

Secondary binary outcomes will be analysed in the same procedure, initially as intention to treat with all eligible patients as the denominator and then to explore the steps in the pathway by per protocol analysis in particular to analyse on treatment success:

- a) Proportion of HCV tested.
- b) Proportion who start HCV treatment within the duration of the study of those identified with HCV.

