### 9.3 MISSING DATA

The nature of this trial is to assess the applicability of this model in the real world, so incomplete data that impacts the primary outcome will be assumed to be consistent with failure of therapy and drop-outs won't be replaced. However every effort will be made to obtain missing data and as the primary outcomes are not time point critical a wide latitude for admissibility of data will be employed. We will accept measures of SVR up to 12 weeks after the due SVR12 date.

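### The drop-out allowance in section 9.1 assumes that drop-outs leave the analysis, but sections 9.2.3 and 9.3 count them as failures, so the 90% power does not follow for such losses

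*Protocol*

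**What the plan says.** Section 9.1 assumes a 95% SVR rate in the DOT arm, citing published studies. With a non-inferiority limit of 14%, a 5% significance level and 90% power it arrives at 42 per group, 126 in total. It then adds: "To allow for drop-outs we will aim to recruit 135 individuals, 45 per group".

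Other sections fix how drop-outs enter the primary analysis:

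- Section 9.2.3 sets the denominator: "the denominator will be total number of patients randomised to each arm".
- Section 9.2.3 also sets the failure rule: "we will assume that drop-outs / lost to follow-up are failures, there will be no missing data in the primary outcome".
- Section 9.3 repeats the rule: "incomplete data that impacts the primary outcome will be assumed to be consistent with failure of therapy and drop-outs won't be replaced".
- Section 4.1 fits with this, though it does not itself call them SVR failures: "trial dropouts are a trial endpoint and will not be replaced".
- Section 9.2.1 describes the SVR comparison as made "in 135 new HCV positive individuals randomised to one of three groups".

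The Summary names a different set: "Analysis will be by modified intention to treat of all participants who receive one dose of therapy". The two sets can differ in practice, because section 5.5.1 says of people who have been randomised: "They may then not be seen at the needle exchange for a number of weeks or even months".

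**The concern.** Raising 42 to 45 is the usual n/(1 − d) inflation. It works when lost participants are removed and 42 per group remain with the assumed success rate. Under sections 9.2.3 and 9.3 nobody is removed. A lost participant stays in the denominator as a failure, which moves the SVR rate away from 95%, raises the binomial variance and widens the confidence interval against a fixed 14-point margin. The allowance corrects for a loss of numbers that the analysis does not permit, and leaves uncorrected the fall in SVR that the analysis does produce.

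The stated 90% justifies the size of the trial and governs how a failure to show non-inferiority will be read. If true power is nearer two in three, an inconclusive result is quite likely even when the arms are identical, while readers would take that risk to be one in ten.

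**Working it through.** **Inputs.** From section 9.1: SVR p = 0.95, margin 0.14, 5% level, 90% power, 42 then 45 per group. Assumed: equal true rates in the two arms compared (this reproduces the protocol's figure) and one unadjusted comparison. Section 9.2.3 plans a logistic model adjusted for therapy and genotype, so the figures are illustrative.

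**Reproducing the protocol's figure.** n = (z₁₋α + z₀.₉₀)² × 2p(1 − p) / 0.14².

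- One-sided 5%: (1.645 + 1.282)² × 2 × 0.95 × 0.05 / 0.0196 = 41.5, so 42. This matches.
- Two-sided 5%: 50.9, so 51. This does not match, so the 5% must be one-sided.
- Allowance: 3/45 = 6.7%, and 42 / (1 − 0.067) = 45. The inflation itself is arithmetically sound.

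**Power under the failure rule.** Let j be the expected number per arm without an SVR sample, and let 95% be the SVR rate among the rest. Then p = 0.95 × (45 − j)/45, and power = Φ(0.14 / √(2p(1 − p)/45) − 1.645). For j = 3: p = 0.95 × 42/45 = 0.8867, standard error 0.0668, and Φ(2.095 − 1.645) = 0.674. The last column is exact binomial enumeration of the Wald test.

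| Expected losses per arm | SVR | Power | Exact |
|---|---|---|---|
| 0 | 95.0% | 0.920 | 0.899 |
| 1 | 92.9% | 0.826 | 0.816 |
| 2 | 90.8% | 0.742 | 0.742 |
| 3 | 88.7% | 0.674 | 0.681 |
| 4 | 86.6% | 0.619 | 0.630 |
| 5 | 84.4% | 0.574 | 0.588 |

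At 45 per arm, 90% power needs an SVR of about 94.6%, so one expected loss per arm is already too many. At 88.7% SVR, 90% power would need 87.8, so 88 per arm. If exactly 3 are lost in each arm, with no chance variation in that number, exact power is 0.757.

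**Other readings of the protocol.**

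- *95% already counts losses as failures:* power at 45 per arm is 0.920 (exact 0.899), and no allowance is needed to hold about 90%.
- *That reading together with an expected 3 losses per arm:* SVR cannot exceed 42/45 = 93.3% even if everyone else is cured. Power is then at most 0.846 (exact 0.834).
- *One-dose set from the Summary, all 3 lost before dosing:* n = 42 and p = 0.95, giving 0.903 (exact 0.912). This is the case in which the allowance does its job.

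**Unequal loss.** With 6.7% lost in one arm only (88.7% against 95%), power is about 38% if the loss is in the fortnightly arm and about 97% if it is in the DOT arm.

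**The case against.** The best defence is that section 9.1 speaks of the SVR rate in this trial's DOT arm and in this population. In this trial SVR counts losses as failures, so 95% could be the net rate, power would be about 92%, and the extra 3 would be harmless. This reading is open, but the same sentence bases the figure on published studies, and adding an allowance suggests that drop-outs were not yet included. The text is ambiguous, so the 67% is conditional.

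A second defence is that dropping out of treatment is not the same as lacking an SVR sample. Sections 6.3 and 6.4 keep participants in follow-up after treatment stops, and section 9.3 accepts samples up to 12 weeks late. True losses may be few, and the protocol gives no rate. That stands, and it also limits the 93.3% ceiling, which assumes that the 3 extra per arm are the expected number without a sample. Yet one such loss per arm is enough to take power below 90% if 95% is the rate among those who stay.

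Third, the one-dose set in the Summary rescues losses before dosing. It does, but it contradicts section 9.2.3, and losses after the first dose remain failures under either set.

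Finally, equal loss in both arms is an assumption. Section 1.2 says that DOT may put people off taking up therapy, so unequal loss is foreseeable. This widens the range in both directions and does not remove the mismatch.

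**Conclusion.** The point holds. The reason given for going from 42 to 45 per group does not fit the failure rule that the protocol itself fixes, and this mismatch does not depend on any assumed loss rate. The effect on power does. The 90% stands, at least approximately, if losses occur before dosing and the one-dose set governs, if nobody lacks an SVR sample, or if 95% is already net of failures with fewer losses than the allowance. It does not stand for the case that the allowance appears to cover under section 9.2.3: about 3 per arm without a sample, counted as failures, with 95% among the rest. Power is then about 67%, assuming equal losses, equal true rates, one-sided 5% and no adjustment. Because no drop-out rate is stated, 67% is not a floor. The denominator, the failure rule and the sample-size rationale are all set in the protocol, so a separate analysis plan would not resolve the conflict. It should be fixed.

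**What to change.** 1. Reconcile the Summary with section 9.2.3 so that one primary analysis set is named.
2. State in section 9.1 whether 95% is the SVR rate with drop-outs counted as failures or the rate among participants who provide a sample.
3. Replace the drop-out inflation sentence with the power at 45 per arm under the rule actually used. Give the assumed proportion without an SVR sample in each arm, and say that the 5% level is one-sided. A short range of loss rates, including unequal loss, would serve the reader best.

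The cost is wording in the Summary and sections 9.1 and 9.2.3. The sample size stays at 135 and no clinical procedure changes. The stated power may become less favourable: the change discloses the power and does not restore it.
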